10.6 Statistical Methods

10.6.1 Primary Efficacy Endpoint Analyses

The primary endpoint is the percentage of treatment responders at Month 24.

Main analysis of primary endpoint

The percentage of patients fulfilling the criteria for treatment response (primary efficacy endpoint), as obtained after applying the rules for replacement of post-baseline missing data detailed in the SAP, will be presented by treatment group.

The primary efficacy endpoint will be compared between the two treatment groups by means of a Chi square test or a Fisher's exact test (as appropriate). The relative risk (PREOB® vs. Placebo) will be reported along with the associated confidence interval. The difference between the two groups will be considered significant if the *p*-value is lower than the significance level as defined in Section 10.7.

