The full analysis set (FAS) consists in an modified Intention-To-Treat population and will be considered as the primary cohort for analysis of efficacy.

The superiority of PREOB® over Placebo will be considered achieved if the percentage of treatment responders is statistically significantly higher in the PREOB® group than in the Placebo group at Month 24. The primary efficacy endpoint will be compared between the two groups by means of a Chi square or a Fisher's exact test (as appropriate). The difference between the two groups will be considered significant if the *p*-value is less than or equal to the Type I error.

Comparison between treatment groups of the secondary binary efficacy endpoints will be performed at each studied timepoint, by means of a Chi square test or a Fisher's exact test (as appropriate). Treatment effect over the 24-month follow-up period will be assessed using a Generalized Estimating Equations (GEE) model taking into account correlations between the repeated measurements within patients.

Comparisons between treatment groups of the secondary continuous efficacy endpoints will be performed at each studied timepoint by means of a parametric Student t-test or a non-parametric Wilcoxon rank-sum test (as

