1 INTRODUCTION

1.1 Background of the Study

1.1.1 Osteonecrosis of the Femoral Head

Non-traumatic osteonecrosis, also known as avascular necrosis, is a bone disease characterized by necrosis of bone and medullary tissues, mainly at bone epiphyseal sites evolving towards articular collapse and joint destruction due to non-traumatic aetiological factors.

Osteonecrosis is a devastating disease with a dramatic natural evolution. Osteonecrosis mainly affects young patients (30-60 years old, with only 20% of patients older than 50 years of age). Natural history of symptomatic osteonecrosis of the femoral head is generally characterized by relentless progression to collapse of the femoral head, ultimately leading to total hip arthroplasty. Based on current practice and available therapeutic options, nearly one-half of patients will require total hip arthroplasty (THA) before the age of 40. Studies have shown that within two years, 93% of stage I and 70% of stage II osteonecrosis in untreated patients will show radiological progression, with a mean progression time of respectively 8 and 14 months, which ultimately leads to femoral head collapse thus requiring total hip arthroplasty (Steinberg *et al.*, 1997; Steinberg *et al.*, 2001).

Non-traumatic osteonecrosis is generally associated with one or more risk factors. In Caucasians, over two thirds of non-traumatic osteonecrosis are associated with past or current corticosteroid therapy and/or alcohol overconsumption. The remaining third includes dysbaric phenomenon, haemoglobinopathies, and coagulopathies. In other rarer medical conditions, the incidence of non-traumatic osteonecrosis is known to be greater than 1%, including organ transplant recipients and patients with systemic lupus erythematosus (Vail & Covington, 1997). Idiopathic cases account for a small proportion of non-traumatic osteonecrosis (<5%).

The exact incidence of osteonecrosis is unknown, but osteonecrosis is the underlying diagnosis in about 5% to 12% of total hip arthroplasty (Lieberman *et al.*, 2003). With an average time to hip arthroplasty of less than two years, the estimated prevalence of osteonecrosis in the OECD countries ranges from 2.5 to 3.1 per 10,000 habitants.

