2.3.3 Randomisation

Eligible patients will be randomly assigned to one of the two study treatments, PREOB® or Placebo, in a 1:1 ratio.

PREOB-ON3 - Clinical Study Protocol

PREOB-ON3-CSP	V 6.1	Author: [name]	May 15, 2017	Pg. 41/42
---------------	-------	----------------	--------------	-----------

Patients will be allocated a Patient Randomisation Number via the randomisation process (through the eCRF). Stratification according to ARCO Stage I or Stage II will automatically be made at the time of randomisation.

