10.4 Sample Size

The single sample size test is planned with a two-sided 5% significance level and a power of 90% assuming the use of Chi-square test (see Table 14). The proportion of treatment responders

PREOB-ON3 - Clinical Study Protocol

PREOB-ON3-CSP V 6.1 Author: [name] May 15, 2017 Pg. 87/88

is assumed to be equal to 63% for the PREOB® group and 30% for the Placebo group. These hypotheses have been estimated on the basis of the Phase IIb data set.

Table 14: Sample size estimation - Chi-square test

Test?	Chi-square
Test significance level, α	0.05
1 or 2-sided test?	2
Group 1, PREOB® proportion, π_1	0.63
Group 2, Placebo proportion, π_2	0.30
Power (%)	90
N per arm	46

A Chi-square test with a 5% two-sided significance level will have 90% power to detect the difference between a Group 1 proportion, π_1 , of 0.63 and a Group 2 proportion, π_2 , of 0.30 when the overall sample size is 92 patients (46 patients in the PREOB® group and 46 patients in the Placebo group).

As an interim analysis is planned in the study using a group sequential design approach, the maximum sample size must be increased to achieve the desired power of 90% at final analysis. The increase in sample size depends on the overall significance level, the statistical power, the number of interim analyses and the type of boundaries being used (See section 10.7). Thus, the maximum sample size is obtained by multiplying the above fixed sample size by a constant determined by these parameters. For the current study, the maximum sample size is 110 patients (1.19 * 92 patients).

Taking into account a drop out and lost to follow-up rate of 7.5%, the overall sample size should be of 118 patients (59 patients in the PREOB® group and 59 patients in the Placebo group) to ensure around 110 evaluable patients at Month 24.

Sample size was computed using the procedure seqdesign of SAS® software version 9.2.

Additional considerations for sample size estimation

Although no claim is intended for the comparison of efficacy endpoints other than the primary endpoint, sample size calculations have been conducted to ensure that such comparisons may be performed with sufficient power to provide additional characterization of the treatment effect and yield supportive evidence related to the primary objective.

PREOB-ON3 - Clinical Study Protocol

PREOB-ON3-CSP

V 6.1

Author: [name]

May 15, 2017

Pg. 88/89

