10.7 Interim Analysis

A Data Safety Monitoring Board (DSMB) will be responsible for reviewing accumulated safety and efficacy data at intervals throughout the study.

In particular, the DSMB will evaluate the results of a formal pre-planned interim efficacy analysis in order to assess the efficacy effect of PREOB® versus Placebo with the intent to stop the study early if there is overwhelming evidence of treatment benefit or futility. The DSMB will recommend to the Sponsor whether to continue, modify or stop the clinical trial based on efficacy or futility but also on safety issues or other considerations not related to efficacy or safety.

The interim analysis will be performed after approximately 40% of required patients have been included in the study with available efficacy data at 12 months. A group-sequential stopping boundary will be used to preserve the overall Type I error rate at 5%.

The Lan-DeMets (Lan *et al.*, 1983) alpha-spending approach will be applied with Pocock (Pocock *et al.*, 1977) stopping boundaries to evaluate the difference in proportions of treatment responders between the treatment groups. A significance level of 0.01341 on the upper and lower boundaries will be used for the interim analysis to support early termination for efficacy. The significance level at the final analysis is expected to be of the order of 0.01341 on each of the upper and lower tails. Significance levels may be adjusted depending on the exact number of patients evaluated at the interim analysis. Futility will be assessed with conditional power (Lachin *et al.*, 2005), *i.e.*, probability of success at the end of the trial given the interim results.

To provide the DSMB with supporting data for recommendation following review of results of the interim analysis, the DSMB may request the analysis results for main secondary endpoints. If the study is stopped based on the recommendation of the DSMB, then all planned analyses will be performed according to what is described for the final analysis in this protocol and the SAP.

The Sponsor and other trial personnel will receive the DSMB recommendations only. No analysis results on the interim results will be communicated.

The specific activities of the DSMB as well as statistical procedures and rules for interim and final analyses are further described in the SAP and the DSMB charter.

PREOB-ON3 - Clinical Study Protocol

PREOB-ON3-CSP

V 6.1

Author: [name]

May 15, 2017

Pg. 91/92

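### Randomisation is stratified by ARCO stage but the primary test ignores stage; if stage is prognostic, the test is conservative and gives up about 0 to 2 points of power at the planned rates.

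*Combined protocol and SAP*

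**What the plan says.** Section 2.3.3 (Randomisation) allocates 1:1 and adds: "Stratification according to ARCO Stage I or Stage II will automatically be made at the time of randomisation". Stage is the only stratification factor named.

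Section 10.6.1 names the primary test: "The primary efficacy endpoint will be compared between the two treatment groups by means of a Chi square test", with Fisher's exact test as the alternative, and reports a relative risk with its confidence interval. The synopsis agrees: "The primary efficacy endpoint will be compared between the two groups by means of a Chi square". Section 10.4 sizes the trial for the same unstratified test, with "a two-sided 5% significance level and a power of 90% assuming the use of Chi-square test". Section 10.7 compares responder proportions at the interim and mentions no strata: "A significance level of 0.01341 on the upper and lower boundaries will be used for the interim analysis". About the same level is expected at the final analysis.

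No readable part of the protocol puts stage into the primary comparison or explains why it is left out. On prognosis, Section 1.1.1 states that within two years "93% of stage I and 70% of stage II osteonecrosis in untreated patients will show radiological progression". Section 10 leaves detailed methods to a separate SAP, which was not among the documents reviewed.

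**The concern.** Stratified randomisation makes the arms alike on stage. If stage also predicts response, the difference in responder rates varies less from trial to trial than it would under simple randomisation. The unstratified chi-square does not use this. Its pooled variance counts the spread between stages as noise, so the standard error is too large and the true rejection rate under the null falls below nominal.

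What is at stake is efficiency. The sponsor already collects stage and balances on it, and the named test takes no advantage. If stage is not prognostic for the composite endpoint, nothing is lost.

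**Working it through.** **Inputs from the protocol.** 63% v 30% responders; 46 per arm fixed, 110 maximum (55 per arm), 118 randomised with 7.5% loss (Section 10.4); 0.01341 per tail, so 2 × 0.01341 = 0.0268 two-sided, and an interim at about 40% (Section 10.7), 0.40 × 110 = 44, or 22 per arm.

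**Assumptions not in the protocol.** Stage I share 10–50%; stage odds ratio on the composite response 1 to 5.7; treatment odds ratio constant across stages; strata balanced between arms.

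**Reproducing the plan's figure.** Pooled-variance formula with p̄ = (0.63 + 0.30)/2 = 0.465:

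n = [1.960 × √(2 × 0.465 × 0.535) + 1.282 × √(0.63 × 0.37 + 0.30 × 0.70)]² / 0.33² = (1.3825 + 0.8531)² / 0.1089 = 45.9, so 46 per arm, as stated (power 90.07%). Then 1.19 × 92 = 109.5, so 110, also as stated.

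**Size of the stage effect the text could suggest.** From Section 1.1.1, (0.93/0.07) / (0.70/0.30) = 13.29/2.33 = 5.7. This is used as an upper case, not as an estimate for this endpoint.

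**Why the test is conservative.** With stage I share f, stage rates p₁ and p₂ and overall rate p:

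p(1 − p) = f p₁(1 − p₁) + (1 − f) p₂(1 − p₂) + f(1 − f)(p₁ − p₂)²

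The chi-square uses the whole left side. With balanced strata, the true variance of the difference contains only the first two terms on the right. Example: overall 30%, f = 0.5, odds ratio 5.7 gives stage rates of 13.3% and 46.7%. The last term is 0.25 × 0.334² = 0.0278, so the variance ratio is 1 − 0.0278/0.21 = 0.867. The critical value 2.214 then acts like 2.214/√0.867 = 2.38, a true two-sided level of about 1.7% instead of 2.7%.

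**Power at the final analysis.** Simulated, at least 200,000 trials per scenario; 55 per arm, 63% v 30%, single look at 0.0268, stage I share 10–50%:

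| Stage odds ratio | Chi-square | CMH | CMH gain (points) |
|---|---|---|---|
| 1 | 91.0% | 91.0% | 0 |
| 2 | 91.0–91.3% | 91.0–91.4% | 0–0.1 |
| 3 | 91.1–91.7% | 91.2–92.3% | 0.1–0.7 |
| 5.7, either direction | 91.3–92.7% | 91.5–94.8% | 0.2–2.3 |

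Type I error at odds ratio 5.7, nominal 2.7%: chi-square 1.6–2.6%, CMH 2.5–2.7%.

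**Other settings.**
- Two looks (22 then 55 per arm, 0.01341 per tail): the gain is 0–0.1 points at odds ratio 2, 0–0.6 at 3 and 0.1–2.1 at 5.7. Chi-square power stays at about 92% or above.
- 59 per arm with 7.5% random loss: at odds ratio 1, 90.4–90.6% (chi-square) v 90.2–90.4% (CMH); at 5.7, CMH gains 0.6–2.5 points.
- True rates of 55% v 30%, outside the plan: CMH gains about 1–5 points with a 20–30 point placebo gap between stages and a stage I share of 20–40%.
- Interim, 22 per arm, Month 12 rates taken as equal to Month 24 rates: CMH changes power by −1 to +0.7 points at odds ratios 1–2 and by −0.4 to +8 at 5.7. Its type I error stays at 2.5–2.7%.

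**The case against.** The strongest reply is that the plan is valid and consistent as written. The named test matches the test used for sample size, type I error is protected, and chi-square power at the planned rates never falls below 90.4% in any final-analysis setting with the planned sample size. The loss exists only relative to a different test. That is correct, and it limits the point to efficiency.

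The second reply is that 5.7 does not describe this endpoint. Section 1.1.1 concerns untreated patients and radiological progression. Section 1.2 describes progression as an advance in ARCO stage, so a move from stage I to II may be counted there, yet it is not a failure under Section 10.1.1. Entry rules for pain and lesion angle also differ by stage (Section 2.3.2). In the Phase IIb study (Section 1.1.3.2), 20% and 40% of hips had progressed to fracture at two years while non-response was 100 − 70.0 = 30.0% and 100 − 36.7 = 63.3%, so pain drives much of the composite. Nothing in the protocol links pain response to stage. This also stands: for odds ratios up to about 2 the gain is negligible, and the upper end of the range needs both a very strong stage effect and a sizeable stage I share.

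Third, the SAP may add stage-adjusted analyses. It may, but Section 10.6.1 names the primary test outright, and a supportive analysis would not change it.

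Last, CMH is not entirely free: with few stage I patients at the interim it can lose up to about a point. That cost is small and is counted below.

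**Conclusion.** The mismatch is real: allocation is stratified by stage and the stated primary test is not. If stage is prognostic, the test is conservative and gives up about 0–2 points of power under 63% v 30%. The loss is close to zero at a stage odds ratio of 2 or less and approaches 2 points only near 5.7 with a stage I share of about 30% or more. It could reach about 5 points if the true treatment difference is smaller than planned and stage matters strongly. The stage share and the stage effect on the composite are assumptions; the protocol gives neither. This is a low-cost improvement to consider, not an error that threatens the trial. Confidence is medium because the SAP was not available and the prognostic effect is unknown.

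**What to change.** - In Sections 10.6.1 and 10.7, the synopsis and the SAP, make the primary test at both looks a CMH test stratified by ARCO stage as recorded at randomisation.
- Report the Mantel-Haenszel relative risk and risk difference with confidence intervals.
- Keep the unstratified chi-square as a sensitivity analysis. A supportive logistic model with stage is optional.
- Say when an exact test replaces CMH, and make it an exact stratified test, since the current wording leaves the switch to Fisher's test undefined.

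The cost is protocol and SAP wording and a few lines of code, fixed before unblinding. No new data or patients are needed. If stage turns out not to be prognostic, the price is about 0–0.2 points of power at the final analysis under 63% v 30% (up to about 0.5 under 55% v 30%) and 0.5–1 point at the interim.

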10.6.4 Safety Endpoint Analyses

Detailed statistical methodology for the safety analyses will be provided in the SAP.

Safety variables include AEs, SAEs, vital signs, physical examination, laboratory tests and concomitant medications. All safety analyses will be described by treatment group actually received and overall on the SAF. No replacement of missing safety data will be performed.

For each AE reported, the number and percentage of patients will be tabulated based on the MedDRA system organ class and preferred term. Similar tabulations will be performed by

PREOB-ON3 - Clinical Study Protocol

PREOB-ON3-CSP	V 6.1	Author: [name]	May 15, 2017	Pg. 90/91
---------------	-------	----------------	--------------	-----------

relationship to treatment and by severity. AEs will be distinguished between treatment-emergent AEs and non-emergent AEs (*i.e.*, AEs pre-implantation and AEs post-implantation).

Standard summary statistics of clinical and laboratory values, as well as shift tables presenting incidence of physical and laboratory abnormalities will also be provided by treatment group.

10.7 Interim Analysis

A Data Safety Monitoring Board (DSMB) will be responsible for reviewing accumulated safety and efficacy data at intervals throughout the study.

In particular, the DSMB will evaluate the results of a formal pre-planned interim efficacy analysis in order to assess the efficacy effect of PREOB® versus Placebo with the intent to stop the study early if there is overwhelming evidence of treatment benefit or futility. The DSMB will recommend to the Sponsor whether to continue, modify or stop the clinical trial based on efficacy or futility but also on safety issues or other considerations not related to efficacy or safety.

The interim analysis will be performed after approximately 40% of required patients have been included in the study with available efficacy data at 12 months. A group-sequential stopping boundary will be used to preserve the overall Type I error rate at 5%.

The Lan-DeMets (Lan *et al.*, 1983) alpha-spending approach will be applied with Pocock (Pocock *et al.*, 1977) stopping boundaries to evaluate the difference in proportions of treatment responders between the treatment groups. A significance level of 0.01341 on the upper and lower boundaries will be used for the interim analysis to support early termination for efficacy. The significance level at the final analysis is expected to be of the order of 0.01341 on each of the upper and lower tails. Significance levels may be adjusted depending on the exact number of patients evaluated at the interim analysis. Futility will be assessed with conditional power (Lachin *et al.*, 2005), *i.e.*, probability of success at the end of the trial given the interim results.

To provide the DSMB with supporting data for recommendation following review of results of the interim analysis, the DSMB may request the analysis results for main secondary endpoints. If the study is stopped based on the recommendation of the DSMB, then all planned analyses will be performed according to what is described for the final analysis in this protocol and the SAP.

The Sponsor and other trial personnel will receive the DSMB recommendations only. No analysis results on the interim results will be communicated.

The specific activities of the DSMB as well as statistical procedures and rules for interim and final analyses are further described in the SAP and the DSMB charter.

PREOB-ON3 - Clinical Study Protocol

PREOB-ON3-CSP

V 6.1

Author: [name]

May 15, 2017

Pg. 91/92

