10.3.2 Statistical Hypotheses for the Primary Endpoint

The superiority of PREOB® over Placebo will be considered achieved if the percentage of treatment responders is statistically significantly higher in the PREOB® group than in the Placebo group at Month 24 (primary endpoint).

- H0 (null hypothesis): the difference in percentages between PREOB® and Placebo is equal to 0,
- H1 (alternative two-sided hypothesis): the difference in percentages between PREOB® and Placebo is different from 0 (with percentage PREOB® \geq percentage Placebo).

Superiority will be proven if the *p*-value of the statistical test comparing the percentages of treatment responders between PREOB® and Placebo is less than or equal to the Type I error (two-sided) as defined in Section 10.7 in which case the null hypothesis H0 will be rejected in favor of the alternative hypothesis H1.

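### The final significance level printed in protocol 10.7 (0.01341 per tail) does not follow from the spending method named there, and the factor 1.19 in 10.4 cannot be verified without the futility cut-off.

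*Combined protocol and SAP*

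**What the plan says.** Section 10.7 plans one formal interim efficacy analysis, with Lan-DeMets alpha spending, Pocock-type boundaries and an overall two-sided error of 5%. It is timed for when "approximately 40% of required patients have been included in the study with available efficacy data at 12 months". For that look, "A significance level of 0.01341 on the upper and lower boundaries will be used for the interim analysis". For the last look, "The significance level at the final analysis is expected to be of the order of 0.01341 on each of the upper and lower tails". The section adds that "Significance levels may be adjusted depending on the exact number of patients evaluated at the interim analysis" and that "Futility will be assessed with conditional power", with no cut-off, assumed effect or binding status. It closes by saying that "statistical procedures and rules for interim and final analyses are further described in the SAP and the DSMB charter".

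Section 10.3.2 makes 10.7 the source of the success threshold: the p-value must be "less than or equal to the Type I error (two-sided) as defined in Section 10.7". Section 10.6.1 points to the same place. The claim itself is a responder rate "statistically significantly higher in the PREOB® group than in the Placebo group at Month 24 (primary endpoint").

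Section 10.4 starts from a fixed design of 92 patients (63% against 30%, two-sided 5%, 90% power). It says that the multiplier depends on the boundaries in 10.7, applies 1.19 to reach 110, and adds 7.5% for drop-out to reach 118.

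**The concern.** A Pocock-type spending function does not in general return one level for both looks, so the repeated 0.01341 looked like the interim figure carried over to the final analysis. Because 10.3.2 and 10.6.1 take the success threshold from 10.7, the figure matters. A Month 24 two-sided p-value between 0.0268 (2 × 0.01341) and 0.0300 (2 × 0.0150) would fail on the printed level and succeed under the named method after a 41.3% look.

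The multiplier of 1.19 also looked large for a single Pocock-type efficacy look. If it includes an allowance for futility stopping, the planned 90% power depends on a rule whose terms the protocol does not print.

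**Working it through.** **Inputs.** Two-sided alpha 0.05, power 90%, rates 0.63 and 0.30, 1:1 allocation, 92 patients, factor 1.19, 110 patients (10.4); one look at about 40%, Pocock-type Lan-DeMets spending, 0.01341 per tail (10.7). Both looks are taken to test the same endpoint until step 6.

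**1. The plan's own starting figures.** The pooled-variance formula without continuity correction gives 45.9, so 46 per arm and 92 in total, as stated. 1.19 × 92 = 109.5, so 110; 118 × 0.925 = 109.2, consistent with around 110 evaluable.

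**2. Interim level.** Spending per tail is 0.025 × ln(1 + (e − 1)t).
- t = 0.40: 0.025 × ln(1.6873) = 0.01308.
- t = 19/46 = 0.413: 0.025 × ln(1.7097) = 0.01341.

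The printed interim figure is therefore the 41.3% value. A likely origin is 40% of 46 per arm (18.4) rounded up to 19; that is an inference.

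**3. Final level.** The two statistics are bivariate normal with correlation √t. Choose c2 so that P(|Z1| < c1 and |Z2| < c2) = 0.95.

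| Look at | Interim, per tail | Final, per tail | Equal level at both looks | Total error if 0.01341 is used twice |
|---|---|---|---|---|
| 40% | 0.0131 | 0.0152 | 0.0141 | 4.75% |
| 41.3% | 0.0134 | 0.0150 | 0.0142 | 4.73% |

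So 0.01341 at both looks is neither the spending boundary nor the equal-level Pocock boundary.

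**4. Factor for efficacy stopping only.** Factor = θ² / (1.960 + 1.282)², where θ is the drift that gives 90% power over the two looks.
- Named boundary: 1.100 (40%) or 1.102 (41.3%). 1.10 × 92 = 101.2, about 102 patients.
- 0.01341 twice: 1.129. 1.129 × 92 = 103.9, about 104 patients.

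Neither is 1.19.

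**5. Factor and power with futility stopping.** Let conditional power assume the current trend, with cut-off γ. The trial then stops if Z1 < √t × [c2 + Φ⁻¹(γ) × √(1 − t)]. The protocol gives no γ, so these cut-offs are assumptions.
- Named boundary, 40% look: γ = 4% gives 1.191, about 110 patients.
- 0.01341 twice: γ = 2% (40% look) gives 1.190; γ = 2.5% (41.3% look) gives 1.193; about 110 patients in each case.
- Binding Pocock-type beta spending gives 1.194-1.196, but with a final level of about 0.0175-0.0176.
- If conditional power assumes the design effect instead, cut-offs up to 30% leave the factor at 1.10.

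Power at 110 (levels 0.0131/0.0152, 40% look, stop always followed, current trend):

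| Cut-off | none | 1% | 2% | 3% | 4% | 5% | 10% | 20% | 30% |
|---|---|---|---|---|---|---|---|---|---|
| Power | 92.2% | 91.3% | 90.8% | 90.5% | 90.1% | 89.8% | 88.4% | 86.0% | 83.6% |

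**6. If the interim tests the 12-month responder rate.** The correlation between looks becomes √t × ρ, where ρ is the within-patient correlation of 12- and 24-month response. The documents do not give ρ. With no effect at either time, 0.01341 twice and a 40% look:

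| ρ | 1 | 0.9 | 0.8 | 0.7 | 0.5 | 0 |
|---|---|---|---|---|---|---|
| Total error | 4.75% | 4.87% | 4.97% | 5.05% | 5.17% | 5.29% |

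The total passes 5% when ρ falls below about 0.76.

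**The case against.** The best defence is that nothing here is final. Section 10.7 gives the last-look level as approximate and allows the levels to be adjusted to the interim count. Under alpha spending the final level is recomputed in any case. The synopsis and the opening of section 10 make the SAP the main statistical reference, and 10.7 leaves detailed rules to the SAP and DSMB charter. That text is not in the material supplied, so it cannot be said that the operative level or cut-off is absent from the plan. This stands, and it limits the point to figures printed in the protocol. It does not rescue the figure itself: 0.01341 is already the interim value at 41.3% information, and at that fraction the named method gives 0.0150.

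A reader might also infer that 10.4 and 10.7 cannot belong to one design. The documents do not support that. Section 10.7 names conditional-power futility, and 0.01341 at both looks with a current-trend cut-off of 2-2.5% gives 1.19 and about 110 patients, though it spends less than 5%. The supportable statement is that 1.19 cannot be verified.

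Nor do the documents show that the trial is underpowered. Cut-offs of 10-30% put power below 90%, but cut-offs of 1-4% keep it above, and the protocol states neither.

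**Conclusion.** The expected final level of 0.01341 per tail does not follow from the method that 10.7 names. With the same endpoint at both looks it should be 0.0152 after a 40% look or 0.0150 after a 41.3% look. The printed value errs on the conservative side, with 4.73-4.75% spent. The factor of 1.19 exceeds the 1.10 that the efficacy boundary needs. Futility stopping can explain it, but only with a cut-off that the protocol does not print. Power at 110 is about 92% without futility stopping and falls below 90% at an assumed current-trend cut-off of about 5%.

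A reader might conclude that overall error is inflated. On one endpoint it is not. If the interim tests the 12-month rate, 5% is not guaranteed, but the excess is at most about 0.3 percentage points over the assumed correlations with no effect at either time. Which endpoint the interim tests, and the correlation, need to be settled first. Severity is minor: an incorrect and an uncheckable figure, with no demonstrated loss of error control or power.

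**What to change.** In 10.7:
- Replace the final 0.01341 with the level computed from the alpha actually spent: 0.0152 per tail after a 40% look or 0.0150 after a 41.3% look, if both looks test the same endpoint. State the information fraction used.
- State which endpoint the interim tests. If it is the 12-month responder rate, note that the correlation between looks is below √t, that 0.01341 twice is not guaranteed to hold 5%, and compute the final level accordingly.

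In 10.4, either say that efficacy stopping alone needs a factor of 1.10, or give the conditional-power cut-off behind 1.19, the effect it assumes and whether it is binding, with the resulting power at 110.

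Keep 118 enrolled, and carry the same text into the SAP and DSMB charter. The cost is wording and one power calculation, plus the amendment submission and approval that section 11.9 requires for protocol changes.
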